1.3 STUDY RATIONALE

Bertilimumab is the first monoclonal antibody to specifically neutralize human eotaxin-1. Bertilimumab has been shown to inhibit eotaxin-stimulated migration of cells and may therefore be useful in the treatment of human diseases such as BP, where eosinophil accumulation is an important feature.

This study will provide both safety and efficacy data for internal decision-making regarding further development of bertilimumab in BP. A positive proof of concept in this study would be supportive of further development via randomized control trial(s) to demonstrate that bertilimumab is an adequate candidate for maintenance therapy in newly diagnosed patients and patients resistant to corticosteroid tapering with moderate to extensive BP. Its efficacy in newly diagnosed patients would be proven by allowing reduced initial doses of corticosteroids and reduced cumulative dose of corticosteroids by facilitating rapid tapering to 10 mg prednisone equivalent or lower after initial control of BP lesions. Its efficacy in patients resistant to corticosteroid tapering would be proven by allowing patients to be tapered down from corticosteroids without flaring and/or allowing smaller doses of oral corticosteroids to control the disease.

The study will investigate newly diagnosed adult patients and adult patients resistant to corticosteroid tapering with moderate to extensive BP. The treatment period will include three IV infusions of 10 mg/kg bertilimumab on study Days 0, 14 (±2 days) and 28 (±2 days) and a follow-up period up to Day 84 (or Day 118 for males who have had abnormal semen analysis results on Day 0, Day 14 or Day 28) relative to pre-dose Visit 2. Patients will receive concomitant oral steroids during the treatment and follow-up period.

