It has been demonstrated that relatively low doses of corticosteroids (e.g., 30 mg/day) are only partially effective in achieving disease control or complete remission. The rapid onset of steroid action is desired in order to alleviate patient symptoms as quickly as possible while the slower acting biologic takes effect. A key focus in this treatment is the goal is to taper the steroids as rapidly as possible, a difficult feat to achieve with steroids in isolation. Initial treatment with prednisone has therefore been added to bertilimumab treatment. This study is designed to demonstrate that the successful tapering of corticosteroids over a shorter period of time than physicians have been accustomed to will be possible with the administration of bertilimumab, thereby mitigating risks associated with long term steroid use.

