2.2 STUDY ENDPOINTS AND OUTCOMES

Primary Endpoints

Safety Endpoints

Safety will be evaluated on the basis of the following parameters:

- Adverse events (AE)
- Infusion reactions
- Injection site reactions
- Physical examination
- Vital signs (blood pressure, heart rate, temperature)
- ECG
- Concomitant medications
- Laboratory evaluation (hematology, biochemistry, anti-bertilimumab antibodies)

Secondary Endpoints

Efficacy Endpoints

- Proportion of patients who achieve a reduction in the Total Activity Score of the BPDAI score of at least 50%, 75% and 90% at visits 5 (Day 42), 6 (Day 56), 7 (Day 70), or 8 (Day 84) compared to:
 - Screening, if patient is resistant to corticosteroid tapering
 - Visit 2 (Day 0), if patient is newly diagnosed.
- Proportion of patients who have tapered to prednisone dose of ≤10 mg/day at Visit 8 (Day 84) and/or 2 and 4 months after Visit 8 (Day 84)
- Proportion of patients who achieve control of disease activity at Visits 5 (Day 42), 6 (Day 56), 7 (Day 70), or 8 (Day 84)
 - Ocurrol of disease activity is defined as the time when at least two of the following occur: new lesions cease to form, established lesions begin to heal and/or pruritic symptoms start to abate. Control of disease activity will be assessed by the BPDAI and the investigator's assessment of lesion healing.
- Mean time to control of disease activity from:
 - Screening, if patient is resistant to corticosteroid tapering
 - Visit 2 (Day 0), if patient is newly diagnosed
- Change in BPDAI score at each scheduled measurement timepoint compared to:
 - Screening, if patient is resistant to corticosteroid tapering
 - Visit 2 (Day 0), if patient is newly diagnosed
- Change in BPDAI pruritis component (Visual Analogue Scale) at each scheduled measurement timepoint compared to:

- Screening, if patient is resistant to corticosteroid tapering
- Visit 2 (Day 0), if patient is newly diagnosed
- Change in ABQOL score at each scheduled measurement timepoint compared to:
 - Screening, if patient is resistant to corticosteroid tapering
 - Visit 2 (Day 0), if patient is newly diagnosed

Pharmacokinetic (PK) Endpoints

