The study will consist of three periods:

- A screening period of up to 4 weeks
- An open-label treatment period lasting 4 weeks consisting of IV infusion of bertilimumab at Visit 2 (Day 0), Visit 3 (Day 14) and Visit 4 (Day 28)
- A safety and efficacy follow-up period of approximately 56 days (or 90 days for males who have had abnormal semen analysis results for post-dose Visit 2 (Day 0), Visit 3 (Day 14) or Visit 4 (Day 28) compared to pre-dose Visit 2 (Day 0) results); plus a follow-up phone call 2 and 4 months following Visit 8 (Day 84)

Due to the potential effects of long-term and/or high-dose systemic corticosteroid usage on bullous pemphigoid, newly diagnosed patients will be permitted to take systemic oral corticosteroids specifically for bullous pemphigoid only for a period of 4 weeks prior to the first treatment administration (Visit 2 - Day 0) at doses no greater than 40 mg/day prednisone equivalent.

Newly diagnosed patients who have taken systemic oral corticosteroid for bullous pemphigoid longer than 4 weeks prior to the first treatment administration (Visit 2 - Day 0) or at doses greater than 40 mg/day prednisone equivalent at any time are excluded from the study.

For newly diagnosed patients who have used systemic oral corticosteroids for reasons other than bullous pemphigoid, a washout period of 4 weeks prior to the first treatment administration (Visit 2 - Day 0) is required.

For newly diagnosed patients who are taking systemic oral corticosteroids at a daily dose between 40 mg/day and 30 mg/day prednisone equivalent for BP within 4 weeks prior to the first treatment administration (Visit 2 - Day 0), tapering of systemic corticosteroids will be conducted at the discretion of the investigator. However, patients must be on 30 mg/day prednisone equivalent for the first treatment administration (Visit 2 - Day 0). For newly diagnosed patients who are taking less than 30 mg/day prednisone equivalent prior to the first administration day (Visit 2 - Day 0), a stable dose of systemic corticosteroids should be maintained until Visit 2 (Day 0).

Patients who are resistant to corticosteroid tapering are not required to be washed out from oral corticosteroid treatment prior to Visit 2 - Day 0.

The tapering schedule depicted in Table 1 is recommended for the remainder of the study.

Systemic corticosteroid dose (prednisone equivalent) per day

≥30.0-10.1 mg/day

Decrease by 5 mg each week

10.0 − 0 mg/day

Decrease by 2.5 mg each week

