4.1 INCLUSION CRITERIA

- 1. Males or females, ≥60 years of age
- 2. Patients with a Karnofsy Performance Status >40%
- 3. Eligible patients are defined as follows:
 - a. Ideally, those who have not been previously treated for BP. However, the following treatments are permitted for newly diagnosed patients:
 - Systemic oral corticosteroids ≤40.0 mg/day (prednisone equivalent) within 4 weeks prior to the first treatment administration (Visit 2 - Day 0)
 - Topical corticosteroids other than those that are Class 1 or Class 2 (See Appendix
 F) within 2 weeks prior to the first treatment administration (Visit 2 Day 0)

- b. Those patients considered by the investigator to be resistant to corticosteroid tapering, in which case other corticosteroid regimens are permitted including oral and topical corticosteroids. No wash-out period is required.
- c. Have been diagnosed by the following assessments.
 - Clinical evaluation confirming BP
 - Hematoxylin and eosin (H&E) staining of a skin punch biopsy from the edge of a lesion to check the eosinophil make-up (including eosinophil count) of the inflammatory infiltrate
 - Serum testing for anti BP180 and anti BP230 autoantibodies
 - Direct immunofluorescence (DIF) on salt split skin of a skin punch biopsy from a perilesional area to check the linear deposition of IgG and/or C3 on the blister roof (epidermal side)
 - Indirect immunofluorescence (IIF) of the patient's serum to check for the presence of IgG circulating autoantibodies

Although all of these assessments must be performed, ultimate determination of a positive BP diagnosis based on the composite of these indicators is up to the investigator.

In newly diagnosed patients, if any of these assessments have been performed within 4 weeks prior to first treatment administration, the specific assessment will not have to be repeated. In patients resistant to corticosteroid tapering, if either DIF or IIF immunofluorescence assessments have been performed previously, the specific assessment will not have to be repeated. BP Disease Area Index (BPDAI) including Pruritus VAS and MD assessment of lesions and ABQOL should be performed prior to administration of corticosteroids if possible.

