### 1 Introduction

### 1.1 General

Bertilimumab is the first monoclonal antibody to specifically neutralize human eotaxin-1 (eotaxin). Bertilimumab has been shown to inhibit eotaxin-stimulated migration of cells and may therefore be useful in the treatment of human diseases such as Bullous Pemphigoid (BP), where eosinophil accumulation is an important feature.

The purpose of this study is to provide proof of concept for the treatment of BP with bertilimumab. This study will provide both safety and efficacy data for internal decision-making regarding further development of bertilimumab in BP. Its efficacy in newly diagnosed patients would be proven by allowing reduced initial doses of corticosteroids and a reduced cumulative dose of corticosteroids by facilitating rapid tapering to 10 mg prednisone equivalent or lower after initial control of BP lesions. Its efficacy in patients resistant to corticosteroid tapering would be proven by allowing patients to be tapered down from corticosteroids without flaring and/or allowing smaller doses of oral corticosteroids to control the disease.

The study will investigate newly diagnosed adult patients and adult patients resistant to corticosteroid tapering with moderate to extensive BP. The treatment period will include three IV infusions of 10 mg/kg bertilimumab on study Days 0, 14 (±2 days) and 28 (±2 days) and a follow-up period up to Day 84 (or Day 118 for males who have had abnormal semen analysis results on Day 0, Day 14 or Day 28) relative to pre-dose Visit 2. Patients will receive concomitant oral steroids during the treatment and follow-up period.

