### **Prednisone Dose**

All prednisone doses are summarized in either the Concomitant Medications form or the Corticosteroid Therapy Form depending on the protocol version used. Note that modification of prednisone doses at any time during the study was acceptable.

Therefore, both the mean dose throughout the trial and the cumulative dose will be of interest.

The following prednisone dose summaries will be provided:

- 1. For each patient, divide the relevant form records into the periods which are consistent with the study periods:
  - a. Prednisone dose at Visit 2 will be based on all records done between the Visit 2 (including) and Visit 3 (not including). A single (long) record could be split into several records to fit the trial periods. For example, if a record starts before Visit 2 and ends before Visit 3, only the relative part from Visit 2 date onwards will be related to Visit 2.
  - b. Similarly, all other trial visits will be defined, up to Visit 8.
- 2. For each patient and each trial period, calculate the total prednisone dose (mg) taken during this period. Frequency and the length of exposure should be considered in this calculation. (For example, Dose\*Frequency\*Number of Days)

- 3. The mean prednisone dose (mg/day) for each period will be calculated as the total dose in the previous step divided by the period duration (days).
- 4. The cumulative prednisone dose (mg) for each period will be calculated as the sum of the total prednisone dose (mg) over all preceding periods, starting at Visit 2.
- 5. Calculations similar to those described in steps (3) and (4) will be repeated, but with dose adjusted for a patient's weight. The mean weight adjusted prednisone dose (mg/kg/day) for each period will be calculated as the total dose in step (2) divided by the period duration (days) and divided by the subject's weight (kg) obtained at this visit (or the most recent available). The cumulative weight adjusted prednisone dose (mg/kg) for each period will be calculated as the cumulative sum over weight adjusted doses over all preceding visits.
- Reduction (measured continuously) in prednisone mean dose (mg/day) from Visit 2
   (Day 0) to each subsequent visit
- Dichotomous reduction in prednisone mean dose (mg/day) will be defined as
  - O Success "1", if the dose at Visit 8 (Day 84) does not exceed 10 mg/day
  - o Failure "0", otherwise

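### The SAP's binary prednisone reduction depends only on the Visit 8 dose, so a patient who starts at or below 10 mg/day and does not reduce can be coded as a success

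*SAP*

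**What the plan says.** SAP 7.2.1 (Prednisone Dose) defines two reduction variables side by side. The continuous one is the fall in mean daily dose from Visit 2 to each later visit. The binary one is a success "if the dose at Visit 8 (Day 84) does not exceed 10 mg/day" and a failure otherwise. The Visit 2 dose is built from all records from Visit 2 up to, but not including, Visit 3. The other visits up to Visit 8 are built in the same way. The section also notes that doses could be changed at any time.

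The protocol endpoint (2.2) is the "Proportion of patients who have tapered to prednisone dose of ≤10 mg/day at Visit 8", with further time points 2 and 4 months later.

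On starting doses, the documents say:
- Newly diagnosed patients (Protocol 4.1): "Ideally, those who have not been previously treated for BP".
- Newly diagnosed patients already on steroids (Protocol 3.0 and 6.8.1): there is a rule "For newly diagnosed patients who are taking less than 30 mg/day prednisone equivalent prior to the first administration day", which asks for a stable dose until Day 0 and gives no lower limit.
- Other patients (Protocol 4.1): those "resistant to corticosteroid tapering, in which case other corticosteroid regimens are permitted including oral and topical corticosteroids", again with no lower limit.

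SAP 6.2.2 defines the Efficacy population by availability of BPDAI scores alone. The frequency table planned in SAP 9.4.1 adds no restriction by starting dose.

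**The concern.** A variable called a reduction, answering a protocol endpoint about having tapered, should need the dose to have come down. This one does not. A patient who enters at or below 10 mg/day and is still there on Day 84 is a success whatever happened to the dose in between, including an increase within that range.

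At stake is how the proportion is read. Prednisone dose is one of the SAP's main efficacy endpoints, and SAP 1.1 bases part of its efficacy argument in newly diagnosed patients on "facilitating rapid tapering to 10 mg prednisone equivalent or lower after initial control of BP lesions". The study is meant to inform an internal development decision. With no hypothesis test planned, the descriptive proportion is itself the result, and it will be read as a taper rate when some of its numerator may not be tapers.

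**Working it through.** The plan gives no figure to reproduce. Protocol 8.0 plans descriptive statistics only, and the documents contain no sample-size calculation and no distribution of starting doses.

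**Step 1: apply the two SAP 7.2.1 rules to example patients.** The doses (mg/day) are invented and constant within each visit period. Continuous reduction = Visit 2 dose minus Visit 8 dose.

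| Visit 2 dose | Visit 8 dose | Continuous reduction | Binary result |
|---|---|---|---|
| 10 | 10 | 0 | success |
| 5 | 5 | 0 | success |
| 5 | 10 | -5 | success |
| 0 | 10 | -10 | success |
| 30 | 10 | 20 | success |

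Only the last row is a taper to 10 mg/day. The documents permit every starting dose shown.

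**Step 2: effect on the proportion.** Among N patients with a Visit 8 dose, let L start and end at or below 10 mg/day, R start at or below 10 and end above it, and s start above 10 and end at or below it.
- SAP proportion = (L + s)/N
- Taper rate among those who could taper to 10 = s/(N - L - R)

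Each patient in L adds 1/N to the SAP proportion. At N = 15, the ceiling in the protocol synopsis, that is 1/15 = 6.7 percentage points. If nobody starts at or below 10, then L = R = 0 and both expressions equal s/N.

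**Step 3: illustration (assumed counts).** N = 15, L = 5, R = 0, s = 3.
- SAP proportion: (5 + 3)/15 = 8/15 = 53.3%
- Taper rate: 3/(15 - 5 - 0) = 3/10 = 30.0%

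If instead 2 of the 5 low starters end above 10 (L = 3, R = 2), the SAP proportion is 6/15 = 40.0% and the taper rate is still 3/10 = 30.0%. The gap therefore depends on how the low starters end as well as on how many there are.

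**Step 4: which starting dose could be used.** The SAP's Visit 2 value is an average over about 14 days (Days 0 to 13) and can misplace a patient. The timings below are assumed.
- 12.5 mg/day cut to 7.5 on Day 7: (7 × 12.5 + 7 × 7.5)/14 = 10.0. The patient was above 10 on Day 0 but averages 10.
- 30 mg/day begun on Day 10: (4 × 30)/14 = 8.6. The average hides a late start at 30.

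The same happens at the other end if the Visit 8 dose is a period mean: 15 and 5 mg/day for equal times average 10.

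The first dose recorded at any time is no better. Protocol 6.8.2 allows rescue at any point. Take a patient on 0 on Day 0 who starts 20 mg/day for a flare on Day 42 and is at 10 by Visit 8. That patient would count as having tapered from 20 to 10, although the SAP's continuous reduction is 0 - 10 = -10.

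**The case against.** The case for leaving the rule alone has five parts.

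- **The protocol has no starting-dose condition either.** True, and the SAP keeps the protocol's threshold and its Visit 8 time point. But having tapered to a level implies coming down to it, and Protocol 8.0 leaves such details to the SAP.
- **Staying low may itself be a benefit.** Protocol 1.3 and SAP 1.1 count reduced initial and cumulative doses as evidence of efficacy. This stands. It is a reason to report these patients, not to call them reductions.
- **Everyone may start on steroids.** Protocol 1.3 says "Patients will receive concomitant oral steroids during the treatment and follow-up period" and "Initial treatment with prednisone has therefore been added to bertilimumab treatment". Neither statement sets a minimum dose or says when a previously untreated patient begins. They make low starters less likely but do not exclude them.
- **A threshold and a continuous change often differ.** Also true: 30 to 12.5 mg/day is a failure with a reduction of 17.5, and that alone is no fault. The fault is that a success labelled as a reduction can have a reduction of zero or less.
- **The reader can see it anyway.** By-visit dose summaries (SAP 9.4.1), by-subject steroid listings (SAP 9.3.2) and the patient narratives in the protocol synopsis would reveal low starters in so small a study. That limits the harm, but the tabulated proportion stays as it is.

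A reader might go further and infer that the reported taper rate is inflated, perhaps by the 23 points in the illustration. The documents do not support that. They do not say how many patients started at or below 10 mg/day. The SAP proportion is a weighted average of the success rates in low and higher starters, so it exceeds the taper rate only if low starters more often end at or below 10.

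**Conclusion.** The point holds as a matter of definition: under the written rule, an unchanged dose or a rise to no more than 10 mg/day is coded as a successful reduction, and nothing in eligibility, the analysis population or the planned table prevents it. The numerical effect is unknown. It ranges from nil, with no low starters, to 1/N for each low starter who remains low, which is 6.7 points at N = 15 and more per patient if fewer have a Visit 8 dose. The contrast of 53% with 30% rests wholly on assumed counts.

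The consequence is limited because the study is descriptive, safety is the primary objective, and other planned outputs show individual doses. It is still worth correcting, since the proportion bears on the study's stated efficacy argument and the correction is cheap.

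**What to change.** Change the analysis in SAP 7.2.1 and the table in SAP 9.4.1; nothing in patient management changes.

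1. Keep the all-patient proportion, but label it *at or below 10 mg/day at Visit 8*.
2. Add, as the taper result, the proportion at or below 10 mg/day at Visit 8 among patients whose daily dose in effect on Day 0, including a course begun that day, exceeded 10 mg/day.
3. Show in separate rows, outside the taper rate, patients on 10 mg/day or less on Day 0 and patients who first start systemic steroids after Day 0. A course begun for a later flare is then not counted as a taper.
4. For these rows, use the same measure at both ends: the daily dose in effect on the Day 0 date and on the Visit 8 date, not period means.
5. Identify the added rows as additions to the plan. SAP 7.4 refers to a decision made after the study was completed, so the final SAP postdates study conduct.

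The cost is some SAP wording, derived Day 0 and Visit 8 daily doses, and a few table rows. No new data are needed: steroid doses with start and end dates are already recorded (Protocol 5.3.2; SAP 7.2.1 and 9.3.2). The price is a smaller denominator for the taper result and probably a less favourable percentage.

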### 7.2.2 Additional Efficacy Endpoints

### **BPDAI Pruritus Component (VAS) Score**

The following three VAS sub-scores will be defined:

- VAS Sub-Score I: How severe has your itching been over the last 24 hours
- VAS Sub-Score II: How severe has your itching been over the past week
- VAS Sub-Score III: How severe has your itching been over the past month

The Total Pruritus VAS score is defined as the sum over the three sub-scores. If at least one of the sub-scores is missing, the total is not defined.

• Change in BPDAI Pruritus Component (VAS) (sub-scores and total) from baseline to all subsequent visits

### **Control of Disease Activity**

Control of Disease Activity is defined as the time when at least two of the following occur: New lesions cease to form, established lesions begin to heal and/or pruritic symptoms start to abate. The information needed for this endpoint was not collected for

all subjects. Consequently, data will be presented for the individual subjects where the data is available.

### **Quality of Life**

- The autoimmune bullous diseases quality of life (ABQOL) questionnaire total score (auto-calculated in the CRF), by visit
- Change in ABQOL total score from baseline to all subsequent visits.

#### **Flares**

Frequency distribution of patients experiencing a flare, by visit. This data will be provided by assessing the site's completion of the top section of the BPDAI/Pruritus VAS at each visit for each subject.

## 7.3 Pharmacokinetic (PK) Analysis

Descriptive statistics of PK parameters as described in Section 6.2.1 will be performed by Certara, a vendor chosen by Immune Pharmaceuticals. A final report of PK analysis including the definition of each PK parameter will be issued by Certara and included in the final CSR.

